### 6.3.2 *Benefit assessment*

In analogy with a regular phase I study in healthy subjects, there is no direct benefit for the subjects to participate in the study, aside from an oral examination, which may provide them with information on their general state of oral health. Hence, the safety and wellbeing of the subjects are of utmost importance.

The development of new, nicotine-containing products takes place both in the pharmaceutical industry and in the tobacco industry. Parts of the tobacco industry today are moving towards reducing the presence of known harmful substances, other than nicotine, in the products that are being developed. NP products such as ZYN are an example of such a development, and the use, prevalence and variety of these products has increased globally in recent years. NPs constitute a substitute to both combusted or non-combusted tobacco/nicotine-containing inhalation products (*e.g.*, conventional cigarettes, heated tobacco vaporizers or electronic cigarettes) and to oral tobacco products (*e.g.*, tobacco-based snus and moist snuff).

As mentioned in Section [6.1](#), there is a lack of scientific data regarding the effect on the oral environment, specifically variables related to dental caries and periodontal disease for oral nicotine products in general. Thus, the results generated from this study should be of interest not only for the tobacco industry and consumers, but also for lawmakers and the relevant regulatory authorities.

### 6.3.3 *Risk/benefit conclusions*

It is reasonable to assume that NP products will have less harmful effects on oral health than tobacco-based snus products. From that perspective, the aim of the present study is consistent with society's overall goal of reducing the harm caused by tobacco use.

Overall, the potential benefit of developing and thoroughly characterizing improved tobacco-leaf free nicotine preparations is considered to outweigh the minimal risks that the subjects are exposed to in the study.

## 6.4 Risk assessment regarding the COVID-19 pandemic

Current recommendations from the authorities will be considered on a day-to-day basis and a continuous risk evaluation will be made to assess how the COVID-19 pandemic is affecting the study conduct and the safety of the study subjects. This study includes a healthy population. Hence, study participation should not contribute to increased risks on behalf of the safety of the study subjects or the quality of the data collected.

The recommendations from the European Medicines Agency (EMA) (16, 17) as well as the Swedish Medical Products Agency (MPA) (18) regarding the conduct and management of clinical trials during the COVID-19 pandemic will be taken into consideration. Currently identified risks as well as the planned prevention and mitigation actions are detailed in [Table](#)

6.4-1 and in a risk log as part of the Sponsor’s trial master file (TMF). These may be updated in line with prevailing recommendations, as applicable.

**Table 6.4-1 COVID-19 related risks and mitigating actions**

Risks identified	Actions
Subjects will be exposed to the SARS-CoV-2 virus, which may lead to subsequent development of COVID-19.	According to the recommendations by the Public Health Agency of Sweden (Folkhälsomyndigheten), subjects are not allowed to visit the clinic if they have any symptoms (even if not COVID-19 related).
	Subjects are supplied with hand disinfectant to use during visits to the clinic.
Subjects will fall ill with COVID-19 between visits and not be able to show up for study assessments within the assigned time window.	AEs will be followed up by phone.
	Subjects with suspected COVID-19 symptoms will be directed to seek COVID-19 testing.
	Subjects who are tested positive for COVID-19 between visits will be referred to standard hospital care if needed.
New recommended actions by health authorities that may halt the study, such as society lock-down, if the pandemic escalates.	This risk does not affect subject safety.

## 7 STUDY OBJECTIVES AND ENDPOINTS

### 7.1 Primary objective

The primary objective of the study is to compare the impact on dental plaque acidogenicity after 4 weeks of substitution of tobacco-based snus with either ZYN Dry or ZYN Moist.

#### 7.1.1 Primary endpoint

The difference between ZYN Dry and ZYN Moist in terms of changes in dental plaque acidogenicity, assessed by measuring pH in plaques, after substitution of tobacco-based snus for 4 weeks.

### 7.2 Secondary objectives

The secondary objectives of the study are:

1. To compare the effects on dental plaque acidogenicity following tobacco-based snus substitution with either ZYN Dry or ZYN Moist for 4 weeks.
2. To compare the number of cariogenic microorganisms in dental plaque following tobacco-based snus substitution with either ZYN Dry or ZYN Moist for 4 weeks.
3. To compare the amount of plaque following tobacco-based snus substitution with either ZYN Dry or ZYN Moist for 4 weeks.
4. To evaluate the degree of oral mucosal lesions following tobacco-based snus substitution with either ZYN Dry or ZYN Moist for 4 weeks.
5. To compare tooth discoloration following tobacco-based snus substitution with either ZYN Dry or ZYN Moist for 4 weeks.
6. To evaluate the safety and tolerability of ZYN Dry and ZYN Moist in current, daily tobacco-based snus users.

#### 7.2.1 Secondary endpoints

The secondary endpoints are:

1. The difference in dental plaque acidogenicity, assessed by measuring pH in plaques, following tobacco-based snus substitution with either ZYN Dry or ZYN Moist for 4 weeks.
2. The difference in the counted number of cariogenic microorganisms in dental plaque following tobacco-based snus substitution with either ZYN Dry or ZYN for 4 weeks.
3. The difference in the amount of plaque, counted and scored 0-3, following tobacco-based snus substitution with either ZYN Dry or ZYN Moist for 4 weeks.
4. The difference in the degree of oral mucosal lesions, by presence, visual grading, and histopathological evaluation of biopsies, following tobacco-based snus substitution with either ZYN Dry or ZYN Moist for 4 weeks.
5. The difference in tooth discoloration, by means of colorimetry using a colorimeter and by visual shade grading using a shade guide, following tobacco-based snus substitution with either ZYN Dry or ZYN Moist for 4 weeks.

6. Frequency, intensity, and seriousness of AEs.

### **7.3 Exploratory objectives**

1. To compare BoE in saliva following tobacco-based snus substitution with either ZYN Dry or ZYN Moist for 4 weeks.
2. To compare BoE in urine following tobacco-based snus substitution with either ZYN Dry or ZYN Moist for 4 weeks.

The results of the exploratory objectives may not be reported in the clinical study report (CSR).

#### **7.3.1 Exploratory endpoints**

1. The difference in analyzed BoE in saliva following tobacco-based snus substitution with either ZYN Dry or ZYN Moist for 4 weeks.
2. The difference in analyzed BoE in urine following tobacco-based snus substitution with either ZYN Dry or ZYN Moist for 4 weeks.

## 8 STUDY DESIGN

### 8.1 Overall study design and schedule of events

This is an open-label, two-armed, randomized, longitudinal study, designed to assess the effects on dental plaque acidogenicity and other oral variables in current, daily users of tobacco-based snus who completely substitute their snus use with either ZYN Dry or ZYN Moist nicotine pouches (NPs). The IPs are unflavored (Smooth) or flavored (Cool Mint and Citrus) NPs and of different nicotine strengths (ZYN Dry 6 mg and ZYN Moist 9 mg).

The study will include 46 randomized subjects with the aim to achieve 40 fully evaluable subjects. The subjects are healthy male or female tobacco-based snus users aged  $\geq 21$ - $\leq 55$  years who have used tobacco-based snus for  $\geq 1$  year, with a minimum weekly consumption of 3 or more cans. An effort will be made to randomize at least 5 female subjects per treatment arm in the study (each arm consisting of 23 subjects in total).

The subjects report to the clinic for a screening visit (Visit 1) followed by 4 treatment visits (Visit 2-5) on separate days. The screening (Visit 1) will take place within 5 weeks prior to Visit 2 and will include an eligibility check, including evaluations of tobacco/nicotine use, a brief oral examination, urine pregnancy testing (women of childbearing potential only), and collection of medical history. Also, the salivary secretion rate and buffer capacity will be assessed (see [Table 8.1-1](#) for details). At the end of the screening, the subjects will be asked about flavor preferences on IPs.

Before each treatment visits (Visit 2-5; Day -28, Day 0, Day 14, and Day 28, respectively), scheduled at the same time of the day for each subject, the subjects will refrain from approximal tooth cleaning for 48 h and toothbrushing for 24 h prior to the visits. Also, the subjects will be instructed not to eat, drink, chew gum, or any other mouth related procedures 1 h before the visits and during the visits.

On the first treatment visit (Visit 2, Day -28), the subjects will report to the clinic for a routine dental examination (including assessment of the amount of plaque, oral mucosal lesions, and tooth discoloration), and sampling of specimen for counting the number of mutans streptococci and lactobacilli as well as collection of saliva for assessment of BoE. Data regarding dental plaque acidogenicity will be collected before and after a 1 min mouth rinse with 10 mL of a 10% sucrose solution and assessed at 0, 2, 5, 10, 15, 30, 45, and 60 min. Oral hygiene and dietary habits will also be assessed by a questionnaire. Moreover, the subjects will be provided with a standard toothpaste containing fluoride (sodium fluoride-containing toothpaste; 1450 ppm F) that must be used by the subjects throughout the whole study. The subjects will use their regular toothbrush, which may be manual or electric, during the whole study. Finally, the teeth will be cleaned with rotating rubber cup and polishing paste. The subjects will electronically register the number of tobacco-based snus pouches used per day, the timepoints, and the estimated usage time for four weeks (to Visit 3, Day 0).

On the second treatment visit (Visit 3, Day 0), a routine dental examination (including assessment of the amount of plaque, oral mucosal lesions, and tooth discoloration), and sampling of specimen for counting the number of mutans streptococci and lactobacilli as well as collection of saliva and urine for assessment of BoE will be performed. Data regarding dental plaque acidogenicity will be collected before and after a 1 min mouth rinse with 10 mL of a 10% sucrose solution and assessed at 0, 2, 5, 10, 15, 30, 45, and 60 min. A biopsy of the oral mucosa will be collected. Finally, the teeth will be cleaned with rotating rubber cup and polishing paste. Thereafter, the subjects will be randomized to substitute their tobacco-based snus with either ZYN Dry or ZYN Moist for 4 weeks. The subjects will be provided with the

IPs and will be instructed to use the products ad libitum, following their regular pattern of use, and to electronically register the number of ZYN pouches used per day, the time point, and the estimated usage time for four week (to Visit 5, Day 28).

On the third treatment visit (Visit 4, Day 14), a routine dental examination (including assessment of the amount of plaque and oral mucosal lesions), sampling of specimen for counting the number of mutans streptococci and lactobacilli as well as collection of saliva for assessment of BoE. Data regarding dental plaque acidogenicity will be collected before and after a 1 min mouth rinse with 10 mL of a 10% sucrose solution and assessed at 0, 2, 5, 10, 15, 30, 45, and 60 min.

On the fourth treatment visit (Visit 5, Day 28), a routine dental examination (including assessment of the amount of plaque, oral mucosal lesions, and tooth discoloration), sampling of specimen for counting the number of mutans streptococci and lactobacilli as well as collection of saliva and urine for assessment of BoE will be performed. Data regarding plaque acidogenicity will be collected before and after a 1 min mouth rinse with 10 mL of a 10% sucrose solution and assessed at 0, 2, 5, 10, 15, 30, 45, and 60 min. A biopsy of the oral mucosa will also be collected.

AEs will be collected by subject interview from the start of substitution of tobacco-based snus with ZYN (Visit 3) until the last treatment visit (Visit 5).

The total duration for each subject in the study will be 8 weeks, not including the preceding screening period.

See [Table 8.1-1](#) for schedule of events applicable for each treatment visit.

Study assessments are described in Section [11](#).

**Table 8.1-1 Schedule of events**

Events	Visit 1 Screening	Visit 2 First treatment visit (Day -28)	Visit 3 Second treatment visit (Day 0)	Visit 4 Third treatment visit (Day 14)	Visit 5 Fourth treatment visit (Day 28)
Informed consent	X				
Demographics	X				
Medical/surgical history	X				
History of nicotine use	X				
Inclusion/exclusion criteria	X	X 			
Brief oral examination	X				
Salivary secretion rate and buffer capacity	X				
Pregnancy test 	X	X 	X 	X 	X 
Baseline symptoms	X	X			
Question about flavor preferences	X				
Prior and concomitant medications			X		
Oral examination		X	X	X	X
Plaque acidogenicity 		X	X	X	X
Cariogenic microorganisms		X	X	X	X
Amount of plaque		X	X	X	X
Oral mucosal lesions		X	X	X	X
Discoloration		X	X 		X
Collection of saliva		X	X	X	X
Collection of urine			X		X
Oral hygiene and dietary habits questionnaire		X			
Use of standard toothpaste		X	X	X	X
Cleaning with rotating rubber cup and polishing paste		X	X		
Randomization			X		
Handout of IPs			X	X 	
Monitoring of consumption 				X	
Biopsy of the oral mucosa			X		X
AEs			X	X	X

 Confirmation of eligibility criteria.

 Only subjects of childbearing potential.

 Only at the discretion of the Investigator. Only at the discretion of the PI on Visits 2-5.

 Assessed at 0, 2, 5, 10, 15, 30, 45, and 60 min after a 1 min mouth rinse with a 10% sucrose solution.

 Assessed before and after cleaning the teeth with rotating rubber cup and polishing paste.

 Only if necessary and/or if the subjects want to change flavor of the IP.

 Monitoring of the number of pouches (tobacco-based snus respectively IP) used per day, time points, and estimated usage time.

## 8.2 Rationale for study design

This is an open-label, two-armed, randomized, longitudinal study, designed to assess the effects on dental plaque acidogenicity and other oral variables in current, daily tobacco-based snus users who completely substitute their snus with either ZYN Dry or ZYN Moist NPs.

A parallel study design was chosen for comparison of two types of ZYN product categories, ZYN Dry and ZYN Moist.

Randomization will be used to minimize bias in the assignment of subjects to one of the two treatment arms and to increase the likelihood that known and unknown subject attributes (*e.g.*, demographic and baseline characteristics) will be evenly balanced.

## 9 STUDY POPULATION

Prospective approvals of protocol deviations from eligibility criteria, also known as protocol waivers or exemptions, are not permitted.

### 9.1 Recruitment

The subjects will be recruited from CTC's database of healthy volunteers, as well as from strategic marketing campaigns. Advertisements in social media and other media (newspapers, internet, radio, local distribution of flyers *etc.*) will be used to reach the target audience. The advertising texts approved by the independent ethics committee (IEC) will be used to create all the materials (digital, radio and/or print) for recruitment.

### 9.2 Screening and enrolment log

The PI must keep a record of all screened subjects even if they were not subsequently included in the study. This information is necessary to verify that subjects were selected without bias. The reason for screening failure should be stated for all subjects that were screened but not included. The reason for withdrawal should be stated for all subjects that were included but did not complete the study.

A screening number will be allocated to each subject in connection to the informed consent process at the screening visit (Visit 1). The screening number is generated automatically in the electronic case report form (eCRF). The screening number will allow identification of subjects irrespective of their eligibility for the study.

Subjects included and randomized will be assigned a randomization number (101, 102 *etc.*).

### 9.3 Number of subjects

Forty-six (46) subjects will be included in the study. Approximately 60 subjects will be screened with the aim of achieving 46 randomized subjects and 40 fully evaluable subjects. A fully evaluable subject is defined as a subject who has used the IPs for 4 weeks and who has completed all study visits. An effort will be made to randomize at least 5 female subjects to each treatment arm (each consisting of 23 subjects in total), however a minimum of 2 randomized female subjects in each treatment arm will be considered acceptable.

For replacements of subjects who discontinue from the study, see Section [9.8.3](#).

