## 9.9 Randomization

On Visit 3, the subjects will be randomized into two treatment arms (ZYN Dry or ZYN Moist). Within each treatment arm, the subjects can choose flavor and also change the selected flavor during the study. As this is an open-label study, the treatment arm to which each subject is allocated will be recorded in the eCRF. A computer-generated randomization list will be created using SAS Proc Plan, SAS Version 9.4 or later (SAS Institute, Inc., Cary, NC). The randomization list will contain subject number and treatment arm.

The randomization list will be generated by CTC and a copy of the randomization list will be provided to the packing company and to the clinic. The original randomization list will be kept by the randomizer.

Because this is an open-label study, no blinding procedures will be followed.

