### 17.2 Determination of sample size

The primary endpoint is the difference between ZYN Dry and ZYN Moist in terms of changes in dental plaque acidogenicity, assessed by measuring pH in plaques, after substitution of tobacco-based snus for 4 weeks. No formal sample size calculation has been performed as available data for the two study product types are lacking. Based on previous experiences using this method, 20 subjects are considered to generate sufficient data for the purpose of this study. Hence, with an estimated dropout rate of 15% a total of 46 subjects will be randomized to achieve 40 fully evaluable subjects.

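### The protocol aims for at least 5 women in each arm but randomizes from a list that ignores sex, so allocation does not support the aim

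*Protocol*

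**What the plan says.** Section 9.3 (Number of subjects) states: "An effort will be made to randomize at least 5 female subjects to each treatment arm". It gives the arm size as "each consisting of 23 subjects in total" and adds that "a minimum of 2 randomized female subjects in each treatment arm will be considered acceptable". The synopsis and Section 8.1 repeat the aim of 5 per arm but leave out the floor of 2.

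Section 9.9 (Randomization) describes one computer-generated list made with SAS Proc Plan. On its content it says only: "The randomization list will contain subject number and treatment arm". It names no stratification factor and no separate list for women. The study is open-label, and "a copy of the randomization list will be provided to the packing company and to the clinic".

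The protocol gives no expected number or share of women, and no recruitment quota for them.

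**The concern.** A count per arm is a result of allocation. Under the list in Section 9.9, the arm a woman enters depends on her place on the list and not on her sex. An effort by the site can change how many women enter the trial, but it cannot properly change how they divide between the arms. The protocol thus states an allocation outcome and describes a mechanism that takes no account of it.

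Two things are at stake. If only about as many women are recruited as the aim implies, chance will often leave one arm short. And staff who are asked to watch a per-arm count, while holding a list that shows the coming allocations, have both a reason and a means to influence who takes which place. Section 8.2 gives bias reduction as the purpose of randomizing, and this arrangement works against that purpose.

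The point cannot wait for the SAP. Section 17 requires the SAP only before database lock, whereas stratification has to be settled before the first subject is randomized.

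**Working it through.** **Inputs.** Arms of 23, 46 in total; aim of at least 5 women per arm; floor of 2 per arm (all Section 9.3). One list without a sex stratum (Section 9.9). The number of women randomized, W, is not in the protocol, so it is varied.

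**The plan's own figure.** The protocol gives no probability for the sex aim. Its only related figure is the total: "with an estimated dropout rate of 15% a total of 46 subjects will be randomized to achieve 40 fully evaluable subjects". This is reproduced by 40 × 1.15 = 46. Dividing instead gives 40 / 0.85 = 47.06. The small difference does not matter here, and 46 is used throughout.

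**Unstratified allocation.** With 46 subjects split 23/23 without regard to sex, the number of women X in one arm is hypergeometric:

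P(X = x) = C(W, x) · C(46 − W, 23 − x) / C(46, 23).

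The aim is met when X lies between 5 and W − 5, and the floor when X lies between 2 and W − 2. Below W = 10 the aim cannot be met.

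- *Aim at W = 10.* Only X = 5 works: C(10,5) · C(36,18) / C(46,23) = 252 × 9,075,135,300 / 8,233,430,727,600 = 0.278.
- *Floor at W = 4.* Only X = 2 works: C(4,2) · C(42,21) / C(46,23) = 6 × 538,257,874,440 / 8,233,430,727,600 = 0.392.

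| Women randomized | P(at least 5 in each arm) | P(at least 2 in each arm) |
|---|---|---|
| 4 | 0 | 0.392 |
| 6 | 0 | 0.813 |
| 8 | 0 | 0.953 |
| 10 | 0.278 | 0.990 |
| 11 | 0.509 | 0.996 |
| 12 | 0.686 | 0.998 |
| 13 | 0.811 | 0.999 |
| 14 | 0.892 | 1.000 |
| 15 | 0.943 | 1.000 |
| 16 | 0.971 | 1.000 |

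**Sensitivity to the list type.** Simulated unstratified blocks of 2, 4 or 6 give the same picture: about 0.28, 0.69 and 0.89 for the aim at 10, 12 and 14 women. Simple 1:1 randomization is somewhat worse: 0.246, 0.451 and 0.612 at 10, 11 and 12 women.

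**Sensitivity to the female share.** This is an assumption, since the protocol states no share. With share p, the probability that both arms reach 5 is P(Bin(23, p) ≥ 5)². It is 0.07 at 15%, 0.25 at 20%, 0.51 at 25%, 0.75 at 30% and 0.96 at 40%.

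**Allocation stratified by sex with permuted blocks.**

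- *10 women.* Blocks of 2 always give 5/5. Blocks of 4 give 4/4 after eight women, and the last two split 1/1 with probability 4/6 = 0.67. Blocks of 6 give 3/3 after six women, and the last four split 2/2 with probability C(3,2)² / C(6,4) = 9/15 = 0.60.
- *11 women.* Blocks of 2 give 5/5 plus one. Blocks of 4 give 4/4 plus three women who must split 2/1. Blocks of 6 give 3/3 plus five women who must split 3/2. Every case ends 6/5, so the aim is met with certainty, and this holds for larger numbers too.
- *Floor at 4 women.* Blocks of 2 or 4 give 2/2. Blocks of 6 give 2/2 only with probability 9/15 = 0.60.

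**The case against.** The strongest reply is that 5 per arm is a soft aim. The protocol promises an effort, and Section 9.3 accepts 2 per arm in the same sentence. With 10 women that floor is met 99% of the time and with 8 women 95%, so nothing in the protocol is breached if 5 is missed. This stands, and it is why the point is minor.

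Some stronger readings are tempting, and the protocol does not support them.

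- *A reader might infer that the aim will usually be missed.* That is so only with 10 women or fewer. With 11 it is about even, and from 12 it is met more often than not. As the protocol gives no female share, it cannot be said which case applies.
- *A reader might infer that the aim can be met only by steering women to an arm.* Recruiting more women also works: 14 to 16 women give 89% to 97% with allocation untouched, and Section 9.1 describes recruitment campaigns that could be directed at women.
- *A reader might infer that the sites will in fact steer.* The protocol does not ask for it. Randomization takes place at Visit 3, four weeks after Visit 2, with a window of ±2 days (Section 11.1), which limits the timing of individual subjects without removing it. The opening comes from the clinic's copy of the list. Two stratified lists held by the clinic would be just as readable, so stratification alone does not close it.
- *A reader might infer that sex should then enter the primary model.* Section 17.5.1 plans only summary statistics for the primary endpoint, so there is no such model, and the protocol does not say that sex predicts plaque pH.

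**Conclusion.** The point holds as a mismatch between a stated aim and the allocation that is meant to serve it. At the minimum of 10 women that the aim implies, an allocation that ignores sex fails the aim 72% of the time (1 − 0.278). About 15 women are needed to reach 94%, and the protocol states no recruitment number of either size. The floor of 2 per arm is at risk only if very few women are randomized.

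The figures assume 46 subjects split 23/23 with women placed on the list independently of arm. They do not depend on any assumption about effect size or variability, and the number of women is left open because the protocol does not give it. The severity is minor: the primary comparison is not invalidated, and the change is an inexpensive improvement to make before randomization starts.

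**What to change.** - **Section 9.9:** randomize 1:1 stratified by sex, with small permuted blocks within sex (for example, size 4). Blocks of 2 would meet the aim even at 10 women, but they make every second allocation within a sex predictable in an open-label trial.
- **Section 9.3, Section 8.1 and the synopsis:** restate the aim as a total of at least 11 women randomized. With blocks of 2, 4 or 6 within sex, this gives at least 5 per arm. Recruitment is then what the site works on, and the arm is left to the list. The floor of 2 should be stated in all three places or in none.
- **List access:** the clinic's copy of the list is a separate weakness and needs its own remedy, because stratification does not address it.

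The cost is two lists instead of one and possibly slightly unequal arms. With blocks of 4 and 46 subjects the arms would end at 23/23 or 24/22, because the incomplete blocks in the two strata together leave a difference of 0 or 2.
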